# **Study Drug and Clinical Supplies:**

Continue to check that all clinical supplies, such as study drug kits, laboratory kits, and
ancillary supplies (eg, glucometers, glucose strips, ketone strips and control solution, etc) are
available (and within expiry) in sufficient quantities to accommodate the next 2 study visit for
each subject enrolled. Site Managers should be contacted with any questions or concerns
relating to clinical supplies.

# **Study Drug Resupply**

- For subjects who are not able to return to the site for their next scheduled visit, a caregiver or family member may be permitted to receive study drug on behalf of the subject if first discussed and agreed to by the subject or parents/legal guardians. Identification of the individual who is granted permission to receive the study drug on behalf of the subject must be confirmed and documented in the subject's source records and on the study drug accountability forms. The site staff must confirm that the study drug is provided to the appropriate individual while ensuring the proper chain of custody for the study drug and maintaining subject privacy.
- The site staff may deliver study drug directly to subject's home with approval from the IRB/EC overseeing the trial and in accordance with site approved procedures. The chain of custody for the study drug and transit conditions must be documented within the subject's source records.
- If no other alternative is feasible, the Site Manager should be contacted to confirm if local regulations allow for direct-to-subject study drug shipments. Permission from the subject or parents/legal guardians and the Sponsor is required prior to implementing a direct-to-subject study drug shipment and all permissions must be recorded in the subject's source record and on the Comments eCRF using the "COVID-19-related" prefix.

#### **Data Entry and Site Monitoring:**

- The regular assessment and reporting of adverse events and changes in concomitant medications should continue as outlined in the eCRF Completion Guidelines.
- If on-site monitoring is not possible as a result of the COVID-19 outbreak, site monitoring will be performed remotely. Site Managers will schedule on-site or remote monitoring visits as conditions dictate.

To ensure the safety of subjects and their families as well as site staff, the guidance offered in this Appendix is to be followed on a temporary basis at those sites impacted by the COVID-19 outbreak in order to enable continuity of treatment and the continuation of protocol-specified assessments outlined in the Protocol's Time and Events Schedule. Every effort should be made to complete all protocol-required assessments when possible.

Attachment 3:	Clinical Laboratory Tests	34
Attachment 4:	Criteria for Pre-defined Limit of Change (PDLC) and Abnormal Values	36

ABBREVIATIONS

ACR	albumin/creatinine ratio
AE	adverse event
AHA	antihyperglycemic agent
ANCOVA	analysis of covariance
ATC	anatomical therapeutic chemical
BMI	body mass index
CI	confidence interval
CSR	clinical study report
CTx	carboxy-telopeptide
DBP	diastolic blood pressure
eCRF	electronic case report form
eGFR	estimated glomerular filtration rate
EOT/EW	end-of-treatment/early withdrawal
FAS	Full analysis set
FOIA	Freedom of Information Act
FPG	fasting plasma glucose
GCP	Good Clinical Practice
HhA.	Hemoglobin A
HDL-C	high-density lipoprotein-cholesterol
IDMC	Independent Data Monitoring Committee
IWPS	interactive web response system
KM	Kaplan-Mejer
	low density linenrotain chalesteral
LDL-C	Lower Limit of Normal
LLN	last absorbation corrigid forward
LUCI	last observation carried forward
	missing at random
MAK	Manta Carla Markay ahaina
MUMU	Monte Carlo Markov chains
	multiple imputation
	medical history
MedDKA	medical dictionary for regulatory activities
	mixed model for repeated measures
PDLC	pre-defined limit of change
PD	pharmacodynamics
PK	pharmacokinetic(s)
PMM	pattern mixture model
PP	per protocol
PI	preferred term
PIH	parathyroid hormone
SAE	serious adverse event
SAP	Statistical Analysis Plan
SBP	systolic blood pressure
SD	standard deviation
SE	standard error
SGL12	sodium-glucose co-transporter 2
SOC	System Organ Class
SPERT	Safety, Planning, Evaluation, and Reporting Team
TEAE	Treatment-Emergent Adverse Event
T2DM	Type 2 Diabetes Mellitus
ULN	Upper Limit of Normal
UTI	urinary tract infection
WHODD	World Health Organization Drug Dictionary

AMENDMENT HISTORY

Amendment 1 (17 July 2018)

Applicable Section(s)	Description of Change		
Rationale: The reason for this amendment is to include analyses of the primary efficacy endpoint in an			
independently powered subset of subjects on a background of diet and exercise only. Clarifying text is added and			
minor typographical errors are also addressed.			
Section 1.1. Major Secondary Objectives	Major secondary objectives have been updated to reflect the		
	change above.		
Section 1.3. Statistical Hypotheses for Trial	Secondary hypotheses have been updated to reflect the change		
Objectives, (Secondary Hypotheses)	above.		
Section 1.4. Sample Size Justification	The details of the assumptions for the sample size justification		
	have been updated based on adult data from Stenlöf (2013).		
Section 3. Interim Analysis and Data	Section streamlined with reference to the IDMC Charter for		
Monitoring Committee Review	further details.		
Section 5.1.1. Level of Significance	Text and figure describing the multiplicity adjustment have been		
	updated to accommodate the hypothesis testing for the subset of		
	subjects on a background of diet and exercise only.		
Section 5.2.3. Analysis Methods	Text to address the additional analyses of the change in HbA _{1c} in		
	AHA subsets has been added.		
References	The following reference has been added:		
	Stenlöf K, Cefalu WT, Kim KA, et al. Efficacy and safety of		
	canagliflozin monotherapy in subjects with type 2 diabetes		
	mellitus inadequately controlled with diet and exercise. Diabetes		
	Obes Metab. 2013;15(4):372-382.		

Amendment 2 (11 May 2023)

Applicable Section(s)	Description of Change	
The purpose of this amendment is to make this document consistent with Protocol Amendment 4 in terms of the		
analysis specifications and other pertinent details including the primary efficacy analysis based on the pattern		
mixture model. An additional analysis of primary efficacy endpoint using informative Bayesian Prior is add		
due to revised estimates of the treatment effect and the standard deviation specified in the Written Reque		
Amendment 5. This analysis will be performed	d in the event that the study on its own does not yield significant	
results based on primary efficacy analysis. Tw	o additional sensitivity analyses of the primary efficacy endpoint	
are also included. Clarifying text is added as a	pplicable and minor typographical errors are also addressed.	
Section 1.4. Sample Size Justification	This section is updated to make it consistent with Protocol	
	Amendment 4	
Section 5.1.1. Level of Significance	Text and figure describing the multiplicity adjustment have been	
	updated to reflect the deletion of the hypothesis testing for the	
	subset of subjects on a background of diet and exercise only and	
	make it consistent Protocol Amendment 4.	
Section 5.2.2 Estimand	Section updated to be consistent with Protocol Amendment 4	
Section 5.2.3. Analysis Methods	Details of the primary and secondary efficacy analyses of the	
	primary efficacy endpoint using pattern mixture model have been	
	added. Text added to mention that Bayesian analysis of primary	
	efficacy endpoint will be performed in the event the primary	
	efficacy analysis does not yield significant results. Analysis of the	
	primary efficacy endpoint based on copy reference multiple	
	imputation (MI) as well as tipping point analysis have been added	
	as sensitivity analyses. Additionally, supportive analyses have	
	been placed together for further clarity. Other minor editorial	
	changes have been made to provide clarity.	
Section 5.3 Secondary Efficacy Endpoints	Section updated to be consistent with Protocol Amendment 4	
References	The following reference has been deleted as it is no longer	
	applicable:	

Stenlöf K, Cefalu WT, Kim KA, et al. Efficacy and safety of
canagliflozin monotherapy in subjects with type 2 diabetes
mellitus inadequately controlled with diet and exercise. Diabetes
Obes Metab. 2013;15(4):372-382.

Amendment 3 (22 September 2023)

Applicable Section(s)	Description of Change		
The purpose of this amendment is to correct minor inconsistencies at few places in the description of the			
supportive analyses and subgroup analyses. Additionally, clarifying text is added to the description of the			
sensitivity analysis based on mixed model for repeated measures (MMRM).			
Section 5.2.3. Analysis Methods	Changes in the description of the sensitivity analysis based on		
	MMRM.		
	In the description of the sensitivity analysis of the primary efficacy endpoint based on mixed model for repeated measures (MMRM), the following sentence is added to consider other covariance structures in case the model does not converge using the unstructured covariance:		
	"In case the model does not converge using the unstructured covariance then alternative covariance structures (such as compound symmetry and AR (1)) will be considered."		
	Furthermore, since MMRM is not the primary efficacy analysis, the following sentence has been deleted:		
	"This sensitivity analysis will constitute the primary analysis based on a specific health authority request."		
	Changes in the description of re-randomization test		
	Since MMRM will be utilized to perform the re-randomization test, to be consistent, the phrase "primary efficacy comparison" have been replaced with "treatment comparison" as applicable at couple of places since primary efficacy comparison is based on Pattern Mixture Model (PMM) and not MMRM.		
	Changes in the description of subgroup analyses		
	In the paragraph describing the subgroup analyses, the phrase 'primary efficacy analysis' is replaced with 'primary efficacy endpoint' to be consistent since subgroups will be analyzed based on MMRM.		

1. INTRODUCTION

This statistical analysis plan (SAP) contains the definitions of analysis sets, derived variables, and statistical methods for the analyses of efficacy and safety data from the canagliflozin study 28431754DIA3018.

1.1. Trial Objectives

In children and adolescents (≥ 10 to <18 years) with type 2 diabetes mellitus (T2DM) who have inadequate glycemic control (ie, hemoglobin A_{1c} [HbA_{1c}] of $\geq 6.5\%$ to $\leq 10.5\%$), either on diet and exercise only, or on diet and exercise and metformin monotherapy, or on diet and exercise and insulin monotherapy with metformin and insulin.

Primary Objectives

- To assess the effect of canagliflozin relative to placebo on HbA_{1c} after 26 weeks of treatment.
- To assess the overall safety and tolerability of canagliflozin.

Major Secondary Objectives

- After 26 weeks of treatment, to assess the effect of canagliflozin relative to placebo on HbA_{1c} in the subset of subjects on a background of metformin (with or without insulin).
- After 26 weeks of treatment, to assess the effect of canagliflozin relative to placebo on HbA_{1c} in the subset of subjects on a background of diet and exercise only.
- After 26 weeks of treatment, to assess the effect of canagliflozin relative to placebo on:
 - Fasting plasma glucose (FPG).
 - Proportion of subjects with $HbA_{1c} < 7.5\%$, < 7.0%, and < 6.5%.
 - Time to rescue therapy and proportion of subjects receiving rescue therapy.
 - Body weight.
- After 52 weeks of treatment, to assess the effect of canagliflozin relative to placebo on:
 - HbA_{1c} and FPG.
 - Proportion of subjects with $HbA_{1c} < 7.5\%$, <7.0%, and <6.5%.
 - Time to rescue therapy and proportion of subjects receiving rescue therapy.
 - Body weight.

Additional Secondary Objectives

- After 12 weeks of treatment to assess the effects of canagliflozin relative to placebo on HbA_{1c}.
- After 26 weeks of treatment, to assess the effect of canagliflozin 100 mg relative to placebo on HbA_{1c}.
- After 26 weeks of treatment, to assess the effect of canagliflozin 100 mg followed by a dose increase to 300 mg relative to placebo on HbA_{1c}.

- After 26 weeks and 52 weeks of treatment, to assess the effect of canagliflozin relative to placebo on:
 - Body mass index (BMI).
 - Fasting plasma lipids (ie, low-density lipoprotein-cholesterol [LDL-C], high-density lipoprotein-cholesterol [HDL-C], total cholesterol, non-HDL-C, LDL-C to HDL-C ratio, non-HDL-C to LDL-C ratio, and triglycerides).
 - Systolic blood pressure (SBP) and diastolic blood pressure (DBP).
 - Growth velocity and Tanner Staging.
 - Markers of calcium and phosphate homeostasis, (calcium, magnesium, phosphate, parathyroid hormone [PTH], 25-hydroxy Vitamin D, calcitonin; urinary excretion of calcium and phosphate).
 - Bone turnover markers (serum osteocalcin and serum collagen type 1 carboxy-telopeptide [CTx]).
 - Urinary albumin/creatinine ratio (ACR).

1.2. Trial Design

This is a 52-week randomized, double-blind, placebo-controlled, parallel-group study, consisting of a 26-week core double-blind treatment period followed by a 26-week extension double-blind treatment period. Eligible subjects will be either on diet and exercise alone, on diet and exercise and a stable dose of metformin monotherapy, on diet and exercise and a stable insulin monotherapy regimen, or on diet and exercise and a stable combination therapy with metformin and insulin.

Eligible subjects will go directly into a 2-week single-blind placebo run-in period and may then be randomized if they meet all other enrollment criteria. The goal is to have at least 30% of randomized subjects that will be ≥ 10 to <15 years of age, 30% to 75% of participants will be female, and at least 20% in both age subsets (10 to <15 years, and ≥ 15 to <18 years) will be male, and 30% of participants that will have ethnicity and life-style comparable to Europe (these include Greece, Poland, Russia, Brazil and Mexico).

Subjects who meet all enrollment criteria will be randomly assigned in a 1:1 ratio to once-daily administration of canagliflozin 100 mg or placebo and enter a 52-week double-blind placebo-controlled treatment phase consisting of a 26-week core double-blind treatment period, followed by a 26-week double-blind extension treatment period. Randomization will be stratified by antihyperglycemic agent (AHA) background (ie, diet and exercise only, metformin monotherapy, insulin monotherapy, or combination of insulin and metformin) and age group [≥ 10 to <15 years old, ≥ 15 to <18 years old]. Subjects who at Week 12 have an HbA_{1c} of $\geq 7.0\%$ and an estimated glomerular filtration rate (eGFR) ≥ 60 mL/min/1.73 m² will be re-randomized in a 1:1 ratio to either remain on double-blind canagliflozin 100 mg (or matching placebo) or to up-titrate to double-blind canagliflozin 300 mg (or matching placebo).

The total duration of the study, including the 1-week screening phase, the 2-week single-blind placebo run-in period, the 52-week double-blind placebo-controlled treatment phase, and the 30-day follow-up post-treatment phase is approximately 59 weeks for each subject.

1.3. Statistical Hypotheses for Trial Objectives

In children and adolescents (≥ 10 to <18 years) with T2DM who have inadequate glycemic control (ie, HbA_{1c} of $\geq 6.5\%$ to $\leq 10.5\%$), either on diet and exercise only, or on diet and exercise and metformin monotherapy, on diet and exercise and insulin monotherapy or on diet and exercise and combination of metformin and insulin:

Primary Hypothesis

• After 26 weeks of treatment, canagliflozin reduces HbA_{1c} relative to placebo.

Secondary Hypotheses

- After 26 weeks of treatment, canagliflozin reduces HbA_{1c} relative to placebo in the subset of subjects on background of metformin (with or without insulin).
- After 26 weeks of treatment, canagliflozin reduces HbA_{1c} relative to placebo in the subset of subjects on a background of diet and exercise only.

1.4. Sample Size Justification

The primary hypothesis of the study is that canagliflozin is superior to placebo in glycemic control, as measured by the change from baseline to Week 26 in HbA_{1c}.

The sample size calculation is based on the 2-stage randomization design using a 2-sample, 2-sided t-test with Type 1 error rate of 0.05. Based on the following assumptions on treatment effect (0.4% to 0.5% change in HbA_{1c}) and an associated common standard deviation (SD) of 0.9% and assuming 50% of the subjects will meet the re-randomization criteria at Week 12, it is estimated that at least 66 subjects per group will be required to achieve approximately 85% power. To account for attrition due to study discontinuation in a longitudinal analysis (to be described below), a 10% sample size inflation factor is employed (Lu 2008), and a total of at least 146 subjects (73 per arm) will be randomized in this study.

Treatment group	Meeting re- randomization criteria at Week 12	Placebo-subtracted group difference in change in HbA _{1c} from baseline to Week 26
canagliflozin 100 mg to canagliflozin 100 mg	No	0.5%
canagliflozin 100 mg to canagliflozin 100 mg	Yes	0.4%
canagliflozin 100 mg to canagliflozin 300 mg	Yes	0.5%

For subjects who are on background metformin (with or without insulin), it is estimated that at least 33 subjects per group (after accounting for attrition due to study discontinuation) will be required to achieve approximately 85% power to assess the efficacy of canagliflozin on a background of metformin.

Treatment group (add-on to metformin)	Meeting re- randomization criteria at Week 12	Placebo-subtracted group difference in change in HbA _{1c} from baseline to Week 26
canagliflozin 100 mg to canagliflozin 100 mg	No	0.75%
canagliflozin 100 mg to canagliflozin 100 mg	Yes	0.65%
canagliflozin 100 mg to canagliflozin 300 mg	Yes	0.75%

The assumed treatment effect above is based on a subgroup analysis of subjects with baseline eGFR of \geq 90 mL/min/1.73m² from the add-on to metformin study of canagliflozin in adults (ie, Study DIA3006).

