## **Efficacy**

Results of the Phase 3 studies demonstrated the efficacy of canagliflozin in reducing HbA1c in a broad range of adult subjects with T2DM, both with recent onset as well as long-standing diabetes and on a range of different background AHAs. A clinically meaningful improvement in glycemic control was seen when canagliflozin was given as monotherapy and when given in dual combinations (add-on to metformin or to SU agents), in triple oral AHA combinations (add-on to metformin plus an SU agent or metformin plus pioglitazone), in combination with insulin (alone or in combination with other agents), or as an add-on to existing diabetes therapy (any approved oral or parenteral therapy). In the monotherapy study, HbA1c reductions of -0.91% and -1.16% relative to placebo for canagliflozin 100 mg and 300 mg, respectively, were observed. In the studies examining specific add-on combination uses, the efficacy of canagliflozin in lowering HbA1c, relative to placebo, was generally consistent ranging from -0.62% to -0.74% with the 100-mg dose and from -0.73% to -0.92% with the 300-mg dose. Across all studies, the 300-mg dose consistently provided greater HbA1c lowering relative to the 100-mg dose. Because reduction in diabetic microvascular complications is continuous with improvements in glycemic control, the additional glucose-lowering efficacy with the 300-mg dose is considered likely to be clinically relevant.

Results of subgroup analyses performed in a pooled population of the placebo-controlled Phase 3 studies found no important differences when comparing the effect of canagliflozin in change from baseline in HbA1c based on baseline demographic characteristics (age, sex, race, and ethnicity), body mass index (BMI), or geographic region. Greater reductions in HbA1c relative to placebo were observed with canagliflozin among subjects with higher baseline HbA1c and higher eGFR values compared with subjects with lower baseline values. In subjects with moderate renal impairment (ie, baseline eGFRs between 30 to 60 mL/min/1.73m^2), the mean placebo-subtracted reduction in HbA1c was 0.38% and 0.47% on canagliflozin 100 mg and 300 mg, respectively. A

total of 24% and 32% of subjects achieved a target  $HbA_{1c} < 7.0\%$  at the end-of-treatment (EOT) on canagliflozin 100 mg and 300 mg, respectively compared to 17% of subjects on placebo.

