# 11.3.2. Multiplicity Adjustment

To strongly control the family-wise error rate at the 5% significance level, a sequential testing procedure as illustrated in Figure 2 below will be applied. The primary endpoint will be first tested in all subjects (ie, FAS), and if the results are significant (2-sided alpha level of 0.05), it will then proceed to test the subset of subjects on a background of metformin (with or without insulin).

Figure 2: Testing Sequence

The formal hypothesis testing above will be based on all randomized subjects in the FAS.

The comparisons by canagliflozin dose to placebo will also be presented and analyzed using the weights in the analyses described below.

- When comparing subjects who initially receive canagliflozin 100 mg with no dose increase to 300 mg to placebo: All subjects start with a weight of 1. After Week 12, subjects with an HbA1c ≥7.0% and eGFR ≥60 mL/min/1.73m² who are re-randomized to continue canagliflozin 100 mg will have a weight of 2. The subjects who are re-randomized to up-titrate to canagliflozin 300 mg will have a weight of 0.
- When comparing subjects who initially receive canagliflozin 100 mg followed by a dose increase to 300 mg to placebo: All subjects start with a weight of 1. After Week 12, subjects with an HbA1c ≥7.0% and eGFR ≥60 mL/min/1.73m² who are re-randomized to continue canagliflozin 100 mg will have a weight of 0 and those who are re-randomized to up-titrate to canagliflozin 300 mg will have a weight of 2.

As the secondary efficacy endpoints listed in Section 11.3.3, Secondary Efficacy Endpoints, are supportive in nature, no corresponding hypothesis testing will be performed, and therefore they are not included in the testing sequence above.

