5.1. Analysis Specifications

5.1.1. Level of Significance

Unless otherwise specified, all statistical tests will be interpreted at a 2-sided significance level of 5% and all confidence intervals at a 2-sided confidence level of 95%.

To strongly control the family-wise error rate at the 5% significance level, a sequential testing procedure as illustrated in Figure 1 below will be applied. The primary endpoint will be first tested in all subjects (i.e., FAS), and if the results are significant (2-sided alpha level of 0.05), it will then proceed to test the subset of subjects on a background of metformin (with or without insulin).

Figure 1: Testing Sequence

As the secondary efficacy endpoints listed in Section 5.3 are supportive in nature, no corresponding hypothesis testing will be performed and therefore they are not included in the testing sequence above.

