5.2.3. Analysis Methods

Primary Analysis

The primary analysis is based on the FAS dataset, including all HbA1c measurements collected from randomization to Week 26, including the measurements collected after treatment discontinuation or initiation of rescue medication.

The primary analysis will be based on pattern mixture model (PMM), as described below:

- Any intermediate missing data will be multiply imputed using Monte Carlo Markov Chains (MCMC), under a Missing at Random (MAR) assumption.
- Then the participants with ICEs and missing Week 26 HbA1c values will be multiply imputed using a multiple imputation (MI) model based on the participants with ICEs and non-missing Week 26 HbA1c values. An MI regression will be applied to impute all monotone missing values, using treatment group, stratification factors, baseline HbA1c and the change from baseline in HbA1c at Weeks 6, 12 and 20. If this MI model does not converge then a Copy Reference MI model will be used instead, as described in the sensitivity analysis section.
- Any Week 26 missing values for change from baseline in HbA_{1c} in participants without ICEs will be imputed based on the MI regression (see description above) applied to all participants.
- A total of 1000 multiple imputations will be performed. A seed equal to 345 will be used in all MI models.
- After MI, each of the multiply imputed datasets will be analyzed using analysis of covariance (ANCOVA) with terms for treatment, stratification factors, and baseline HbA_{1c}.
- Rubin's rules will be applied to combine the ANCOVA results across the imputed datasets, including the Week 26 LS Means for each treatment group and the difference vs placebo in LS Means.

Secondary analysis of the primary efficacy endpoint

The secondary analysis is based on a subset of subjects on background metformin (with or without insulin) from the FAS dataset, including all HbA1c measurements collected from randomization to Week 26, including the measurements collected after treatment discontinuation or initiation of

rescue medication. The attributes of estimand for this analysis is the same as the primary efficacy estimand except the population is a subset of subjects with background metformin (with or without insulin). The same analysis based on PMM will be performed as described above.

Bayesian analysis of the primary efficacy endpoint

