Bayesian Analysis of the Primary Efficacy Endpoint for overall study and subset of subjects with metformin (with or without insulin) will be performed in the event that the study on its own yields non-significant result based on primary efficacy analysis. Full details of the Bayesian analysis will be included in a separate supplemental SAP.

Sensitivity and supportive Analyses

The following sensitivity analyses will also be performed, all aligned with the primary estimand:

- A Copy Reference MI model will be performed (Ratitch 2013). After any intermediate missing data will be imputed based on MCMC, monotone missing data will be imputed as following:
 - For the canagliflozin group, imputation will be performed using an imputation model based on the placebo/reference group, conditional on the stratification factors, baseline HbA_{1c} and the observed change from baseline values at previous time points relative to the mean of the model for the placebo group. Participants in the canagliflozin group will be imputed as if they had always been members of the placebo group.
 - For the placebo group, imputation will assume Missing at Random.
 - A total of 1000 multiple imputations will be performed. A seed equal to 345 will be used in all MI models.
 - After MI, each of the multiple imputed datasets will be analyzed using ANCOVA with terms for treatment, stratification factors, and baseline HbA_{1c}.
 - Rubin's rules will be applied to combine the ANCOVA results across the imputed datasets.
- A tipping point analysis will also be performed. This analysis starts with a MAR MI model (intermediate missing imputed with MCMC and monotone missing imputed with a MI regression model, using treatment group, stratification factors, baseline HbA_{1c} and the change from baseline in HbA_{1c} at Weeks 6, 12 and 20). Then each imputed value for monotone missing in the canagliflozin group will be made worse by a difference Delta. Each imputed dataset will be analyzed using ANCOVA and Rubin's rules will be applied to combine the ANCOVA results across the imputed datasets. A sequence of Delta worsening adjustments will be applied, starting with zero with increments of 0.1 until the results reach statistical non-significance. The results corresponding to all applied Delta adjustments will be plotted together with the results from the primary analysis, Copy Reference MI analysis and the other sensitivity analyses.

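### Does the 85% power for the metformin subset need restating because that test runs only after a significant result in all subjects?

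*SAP*

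**What the plan says.** SAP 1.4, with the same figures in Protocol 11.2 and the Synopsis, sizes two comparisons separately. For all subjects it takes placebo-subtracted effects of 0.5%, 0.4% and 0.5% for the three dose paths, SD 0.9% and half the subjects re-randomized at Week 12. This gives 66 per group for about 85% power, inflated by 10% to 73. For subjects on metformin the path effects are 0.75%, 0.65% and 0.75%, and at least 33 per group, attrition included, "will be required to achieve approximately 85% power to assess the efficacy of canagliflozin on a background of metformin". The effects are attributed to a subgroup "from the add-on to metformin study of canagliflozin in adults".

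The testing order is given elsewhere. Protocol 11.3.2 tests the FAS first and states that "if the results are significant (2-sided alpha level of 0.05), it will then proceed to test the subset of subjects" on metformin; SAP 5.1.1 has the same rule ("it will then proceed to test the subset of subjects on a background of metformin").

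SAP 5.2.3 schedules the subset analysis without any condition: "The secondary analysis is based on a subset of subjects on background metformin (with or without insulin) from the FAS dataset". It adds a Bayesian analysis of both the whole study and the metformin subset, which "will be performed in the event that the study on its own yields non-significant result based on primary efficacy analysis".

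**The concern.** The metformin subset is the only hypothesis after the primary one in the sequence, so a reader may take 85% as the chance of winning that claim. It is not. To win, the trial must first pass the FAS test, which itself has about 85% power. The joint probability cannot exceed the smaller of the two and will usually be lower.

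The joint figure also needs an input the plan does not give, namely the effect in subjects not on metformin. The two effect tables stand side by side and are not linked. If both are exact, the effect outside the subset is fixed by the metformin share and comes out small. At stake would be an overstated chance of success for the one secondary claim, whose target Protocol Amendment 4 had cut from 37 to 33 per group on the ground that 85% power was kept.

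**Working it through.** **Inputs from SAP 1.4.** Two-sided t-test at 0.05; SD 0.9; 50% re-randomized, split 1:1; 66 evaluable per arm overall; 33 per arm in the subset before attrition; 10% inflation. The SD, the 50% share and the 10% are stated for the overall calculation; carrying them to the subset is an assumption.

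**Average effects.**
- Overall: 0.5×0.5 + 0.25×0.4 + 0.25×0.5 = 0.475.
- Subset: 0.5×0.75 + 0.25×0.65 + 0.25×0.75 = 0.725.

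**The plan's own figures (noncentral t).**
- Overall, effect 0.475, 66 per arm: 85.3%. Inflation: 66×1.1 = 72.6, so 73.
- Subset, evaluable number: 33×0.9 = 29.7, or 33/1.1 = 30. Effect 0.725: 85.4% at 29 per arm, 86.6% at 30.

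Both stated powers reproduce. The subset figure makes no allowance for the gate.

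**Effect outside the subset if both tables are exact.** With metformin share f, the outside effect is (0.475 − 0.725f)/(1 − f).
- f = 30/66 = 0.455: (0.475 − 0.330)/0.545 = 0.27.
- It reaches zero at f = 0.475/0.725 = 65.5% and is negative above that.

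**Probability of passing both tests**, from simulated t-tests with the subset nested in 66 evaluable per arm.

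(a) Overall effect held at 0.475:

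| In subset per arm | Outside effect | Both tests significant |
|---|---|---|
| 29 | 0.28 | 77% |
| 30 | 0.27 | 78% |
| 33 | 0.23 | 80% |
| 36 | 0.18 | 82% |
| 40 | 0.09 | 83% |
| 43 | 0.01 | 83% |

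In the row with 30, the FAS test passes in 84.6% of trials and the subset test is then significant in 92.4% of those: 0.846×0.924 = 0.78. A bivariate normal approximation gives 80% for the same row. With no attrition (73 per arm, 33 in the subset) the simulated figure is 83%.

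(b) Outside effect set directly, 30 in the subset:

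| Outside effect | Implied overall effect | Both tests significant |
|---|---|---|
| 0 | 0.33 | 51% |
| 0.20 | 0.44 | 73% |
| 0.30 | 0.49 | 80% |
| 0.40 | 0.55 | 84% |
| 0.475 | 0.59 | 85% |
| 0.62 | 0.67 | 86% |
| 0.725 | 0.725 | 87% |

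(c) Outside effect set directly, larger subset:
- 33 in the subset, outside 0.30: 84%.
- 35 in the subset, outside 0.30: 86%.
- 40 in the subset, outside 0.20 / 0.30 / 0.475: 88% / 91% / 94%.

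At the minimum size the gate costs almost nothing once the outside effect is about 0.475. Above the minimum size the shortfall against 85% soon disappears, unless the overall effect is pinned at 0.475 or the outside effect is near zero.

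**The case for a change.** The strongest case for a change is that, with the plan's two tables taken at face value, the joint figure stays below 85% at every subset size checked (77% to 83%). No sentence warns the reader that the 85% leaves the gate out. The labelling would cost a few words.

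The arithmetic stands. The reading behind it is less secure. Nowhere does the plan say that 0.475% is a mixture of 0.725% on metformin and something much smaller elsewhere; it may equally be a cautious value for the whole trial. Taken as a mixture, it implies harm outside the subset once the metformin share passes 65.5%. A large share is plausible: the Protocol introduction describes patients on diet and exercise alone as very uncommon.

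The only figures in the documents that bear on subjects not on metformin point the other way. Protocol 1.1.3 reports adult monotherapy "reductions of -0.91% and -1.16% relative to placebo for canagliflozin 100 mg and 300 mg, respectively, were observed", and in the add-on studies the effect "was generally consistent ranging from -0.62% to -0.74% with the 100-mg dose and from -0.73% to -0.92% with the 300-mg dose". These are adult data and the plan does not adopt them as planning values. Still, at 0.62% or more outside the subset the joint power is 86% to 87% at the minimum size, close to or equal to the stand-alone value.

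The SAP amendment history also mentions revised estimates of the treatment effect and SD, set out in a Written Request amendment that is not among these documents. A joint-power table built on the effects now printed might therefore rest on superseded inputs.

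**Conclusion.** No change is needed. The 85% is the correct stand-alone power of the subset test. The sample-size text claims no more than that, and the gate is stated openly in SAP 5.1.1 and Protocol 11.3.2. Giving each hypothesis its own power in a fixed sequence is a fair convention, and a statistician who wants the joint figure can see that the gate applies.

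That joint figure is not one number. It is about 77% to 78% at the minimum subset size if both effect tables are exact, and 73% if the outside effect is only 0.20%. It is 85% or more at the minimum size if the outside effect is at least about 0.475%, and reaches 94% with 40 in the subset and that same outside effect. Only an outside effect near zero would lower it sharply (51% at the minimum size). These figures assume SD 0.9 and 10% attrition within the subset, and use t-tests in place of the planned imputation and ANCOVA.

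Family-wise error control is not affected. A missed FAS test ends the confirmatory claim for the subset, but its analysis is still carried out and the Bayesian analysis is added. Adding the word stand-alone, or an assumed effect outside the subset, would help a reader a little but would change no sample size, alpha, testing order, analysis or conclusion.
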